Awareness and Self-Compassion Enhancing Narcolepsy Treatment (ASCENT)

NCT04306952

11/14/2018

Protocol

Overview of Research Plan

The overall approach taken for this R34 follows recommendations for early stage treatmentdevelopment activities aimed at establishing the parameters of the intervention and research protocols before conducting a full-scale randomized controlled trial (RCT). Building upon our preliminary data, this project focuses on treatment-development, recruitment, and assessment by conducting a feasibility trial to determine the optimal parameters for adapting and delivering an MBI for people with narcolepsy. The first phase of this project consists of preparatory activities, including completion of the study protocol and training of treatment providers. Phase II consists of a feasibility trial in which 60 individuals will be randomized to receive one of three MBI doses of varying length: 4-week MBI (short), 8-week MBI (standard), or 12-week MBI (extended). All MBIs will feature similar content and structure and will be delivered in groups (n=4) using live videoconferencing.

Phase I: Protocol refinement and training of MBI Providers

The main goal of Phase I is to prepare for the feasibility trial. Preparatory activities include refining and completing the MBI protocols, developing a manual of operations, establishing a data and safety monitoring plan, and obtaining IRB approval. We have a preliminary outline of the three MBI doses that will be developed into a formal treatment manual that can be used for training and delivery.

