Phase II consists of a feasibility trial to gather data on the feasibility, acceptability, and clinical impact of MBI. Participants will be randomly assigned to receive one of three MBI doses (short, standard, or extended course) to determine the optimal parameters for length of the MBI program for people with narcolepsy. An important consideration at this stage is to optimize clinical impact and acceptability with cost-effectiveness as a secondary consideration in determining the optimal MBI dose. All MBIs will be delivered in small groups (n=4) using live videoconferencing. Recruitment and screening will begin upon completion of Phase I (month 6)

and we anticipate running 5 cycles. Given the focus on optimization, we will conduct an interim review after completing Cycle 2 to evaluate the need for modifications to the MBI protocol or study protocol. We plan to complete the interventions and assessment in Year 3, between months 6 to 8, leaving the remaining time for data analysis, dissemination of results, and preparation of a U01 or R61/R33 application depending on the findings of this study.

Short MBI (4-week). The short MBI consists of four weekly group sessions that are two hours each and follows the structure and format described above for each group and home meditation practice. Meta-analytic results of MBIs in lifestyle medicine trials have found that intervention effects are not dependent on the length of the MBI and that shorter-length MBIs (< 8 weeks) have demonstrated positive findings with effect sizes similar to MBI of 8 weeks or longer. Therefore, the rationale for testing the short MBI is to evaluate a low-dose (8 hours of contact) MBI that optimizes cost-effectiveness and minimizes patient burden.

Standard MBI (8-week). The standard MBI consists of eight weekly group sessions that are approximately two hours each. Group sessions will follow the structure and format described above. The length of this package is based on the standard length of MBSR as an 8-week program. The rationale for testing the standard MBI is to provide a comparison to a dose (16 hours of contact) that is most similar to the length of MBSR and has the fewest modifications, making it easier to train MBI providers.

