Secondary Considerations. In addition to these benchmarks, we will conduct other analyses as secondary considerations of acceptability and feasibility. We will examine the amount of meditation practice from the daily diaries (total minutes of practice and number of sessions) to assess enactment of mindfulness meditation outside of the sessions. We will conduct qualitative analyses from focus group data using thematic analysis to evaluate themes and patient feedback on each MBI dose. We will also conduct exit interviews with the MBI providers to gather input from the provider's perspective as to the optimal MBI dose. In addition to evaluating effect sizes at post-treatment (Benchmark 3 & 4), we will also conduct linear mixed models to examine the trend of each MBI dose over time (A1 to A4) on SCS, FFMQ, and exploratory clinical measures (ESS, FOSQ, sleep/wake patterns from actigraphy and sleep diaries, neurocognitive assessment). These exploratory analyses will be used to supplement the evaluation of the effect sizes given the variation in time at post-treatment across MBI doses. We will also review adverse events and consider the potential harms as a factor in selecting the MBI condition (i.e., least AEs will be selected). Finally, we will consider the cost-effectiveness of each MBI dose (number of sessions, amount of face-to-face contact, amount of provider training).

Selecting the optimal MBI dose. The major milestone of Specific Aim 1 is to select the optimal MBI condition using the parameters described above. We anticipate that each MBI dose will have a unique profile (e.g., short MBI will have high attendance but smaller effect size on SCS and FFMQ) and will select the MBI dose that is able to achieve the most benchmarks. If these benchmarks cannot determine a condition that is superior, we will use secondary considerations and cost-effectiveness (lowest-level of resources) to determine the optimal MBI dose. This MBI program will be used for further testing or optimization (see Future Directions).

Specific Aim 2: Determine the feasibility of recruitment and assessment methods for MBI using videoconferencing. The purpose of Aim 2 is to evaluate the pace of recruitment and the feasibility of remote data collection using the assessment instruments proposed for conducting a future large-scale trial. We will use the following benchmarks to carry out Aim 2:

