- Benchmark 5 (recruitment feasibility): The benchmark for feasibility of recruitment will be enrollment of 12 participants who meet all eligibility criteria per 3-month cycle (or ≥ 4 participants per month). The criteria for this benchmark is based on the minimum rate of recruitment needed to support randomization into groups of four for each of the MBI conditions. It will provide data to inform recruitment decisions, the method of randomization, and the number of sites needed for a large-scale study in the future.
- Benchmark 6 (assessment feasibility): The benchmark for the assessment protocol is complete data for ≥ 80% of all participants (n=48 out of 60). Completion is defined as providing valid data from baseline (A1) through post-treatment for each MBI. This benchmark will inform the degree of missing data, the acceptability of the assessment protocol (e.g., neuropsychological assessment via videoconferencing), and the selection of instruments (e.g., reliability of collecting actigraphy data remotely).

Secondary considerations. In addition to these benchmarks, we will evaluate the assessment instruments for inclusion in future studies by reviewing the effect size, costs, and patient feedback from focus groups for each instrument. For example, if there is evidence that some PROMIS domains selected for this study are not relevant we will not include these in future studies. We will also examine issues such as practice effects or fatigue to evaluate the validity and feasibility of conducting the neurocognitive battery using videoconferencing for people with narcolepsy. The major milestone of Aim 2 is to establish operational guidelines for effective recruitment methods and an assessment protocol that can be used to support a future large-scale trial.

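### The harms factor in dose selection is a plain count of adverse events, so on that factor a dose with a few serious related events can rank ahead of one with more minor unrelated events

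*Combined protocol and SAP*

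**What the plan says.** Adverse events enter the choice of dose at one place in the supplied text, the Secondary Considerations paragraph under Specific Aim 1. There the plan will review AEs and "consider the potential harms as a factor in selecting the MBI condition (i.e., least AEs will be selected". Nothing in the text separates serious from minor events or related from unrelated ones, or says whether events or participants are counted.

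The paragraph opens by stating the status of everything in it: "we will conduct other analyses as secondary considerations of acceptability and feasibility". The next paragraph, on selecting the optimal dose, gives the order of decision. First, the team "will select the MBI dose that is able to achieve the most benchmarks". Then: "If these benchmarks cannot determine a condition that is superior, we will use secondary considerations and cost-effectiveness (lowest-level of resources) to determine the optimal MBI". No order or weights are given among the secondary considerations, which also include home practice, focus groups, provider interviews, mixed models over time and cost.

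On size, the Overview states that "60 individuals will be randomized to receive one of three MBI doses of varying length: 4-week MBI (short), 8-week MBI (standard), or 12-week MBI (extended". The Phase I section lists a data and safety monitoring plan among the things to be set up; its content is not in the supplied text, and the selection rule does not refer to it.

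**The concern.** The stated purpose is to weigh potential harms. The stated rule is a count in which a cold and a serious event brought on by the intervention each add one. Purpose and rule can therefore point in opposite directions, even if every dose is followed equally long.

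In a behavioural trial with about 20 people per dose, many recorded events may be background illness. A genuine harm signal would add only a few events to that count and carry no extra weight. Between two doses with no related harm, background events alone would settle the comparison. What is at stake is which dose goes forward to further testing in the cases where this factor helps to decide.

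**Working it through.** **Is there a figure to reproduce?** The plan gives no AE rate, threshold or error rate for the harms factor. Only the arm size can be checked. Benchmark 5 requires "enrollment of 12 participants who meet all eligibility criteria per 3-month cycle (or ≥ 4 participants per month", enough for one group of four per condition, and "we anticipate running 5 cycles". So 5 × 12 = 60, which matches the stated total, and 5 × 4 = 20 per dose. Equal allocation is inferred from this, not stated.

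**Can the rule rank the wrong way?** Yes, from the wording alone. Dose A has 2 serious related events and nothing else (total 2). Dose B has 4 minor unrelated events (total 4). Since 2 < 4, A is preferred on this factor. Likewise, 3 serious related plus 4 minor events (7) is preferred to 0 serious plus 8 minor unrelated (8).

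**How often, under assumed rates?**

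Inputs, all assumed:
- Equal follow-up in the three doses.
- Background AEs per dose independent and Poisson with mean m.
- Exactly 2 extra serious related events in one dose.

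With X the background count in the affected dose and Y the count in either other dose:

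- P(strictly fewest) = Σₖ P(X = k) × [P(Y > k + 2)]²
- P(fewest or tied) = Σₖ P(X = k) × [P(Y ≥ k + 2)]²

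For m = 2, the strictly-fewest terms are:
- k = 0: 0.1353 × 0.3233² = 0.0141
- k = 1: 0.2707 × 0.1429² = 0.0055
- k = 2: 0.2707 × 0.0527² = 0.0008
- k = 3: 0.1804 × 0.0166² < 0.0001

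The sum is about 0.020.

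| Background mean per dose | Strictly fewest | Fewest or tied | Tied only (difference) |
|---|---|---|---|
| 2 | 0.020 | 0.082 | 0.062 |
| 4 | 0.066 | 0.143 | 0.077 |
| 6 | 0.099 | 0.174 | 0.075 |
| 10 | 0.141 | 0.207 | 0.066 |

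At a mean of 1 the strictly-fewest figure is about 0.2%. Simulations of 400,000 draws for means 4, 6 and 10 agree to within simulation error.

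**Variant with random harm.** Take 20 per dose, 0.10 to 0.15 serious related events per participant in one dose and none in the others, and 0.2 to 1.0 background events per participant everywhere. Ties are split at random. The affected dose is picked in 8% to 22% of trials on the all-AE count. It is picked in about 2% to 5% if only serious related events are counted.

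**Could the factor come into play?** Benchmarks 1, 5 and 6 (providers, recruitment, data completeness) are set for the trial as a whole. Only Benchmarks 2, 3 and 4 can separate the doses, so each dose scores 0 to 3. Assume independent passes with the same chance p for every dose and benchmark. Let b(k) be the binomial probability of k passes out of 3, and B(k − 1) the probability of fewer than k.

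- P(single top dose) = 3 × Σₖ b(k) × B(k − 1)²
- p = 0.5: 3 × [0.375 × 0.125² + 0.375 × 0.5² + 0.125 × 0.875²] = 0.586, so the top score is tied in 41%
- p = 0.8: 3 × [0.096 × 0.008² + 0.384 × 0.104² + 0.512 × 0.488²] = 0.378, so it is tied in 62%

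Over p from 0.3 to 0.8 the range is about 41% to 62%. These tie chances should not be multiplied by the table. The table compares all three doses, a tie may involve only two, and AEs are then one factor among several.

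**The case against.** The strongest reply concerns reach. Benchmarks choose the dose first, and AEs matter only when those fail to separate the doses, as one unweighted factor. A reader might infer from the parenthesis that the AE count itself selects the dose. The selection paragraph does not support that. This limit stands in full.

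Second, the sentence speaks of reviewing events and considering harms, which leaves room for judgement, and a sensible team would not prefer two serious related events to four colds. This softens the point. But the parenthesis says what the consideration consists of; if judgement is intended, it should not be there.

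Third, AE definitions and grading may sit in the data and safety monitoring plan, or in the Statistical Design and Power section to which the Data Analysis Plan refers. Neither is in the supplied text. A reader might infer that the trial will not grade AEs at all; the documents do not show that. What they show is a selection rule that does not draw on any grading.

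Fourth, the background rates have no source in the documents, and the strictly-fewest figure almost vanishes when background events are rare. In every scenario shown for an otherwise harmless pair of comparators, the affected dose is picked less often than the one-third expected by chance, so the count still leans against it. All of this stands, and it is why the figures are an illustration only.

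**Conclusion.** The point holds in a limited form. As written, the harms factor is the fewest AEs, and on that factor a dose with a few serious related events can rank ahead of one with more minor unrelated events. That follows from the wording and needs no assumed rate.

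How often it would happen does depend on assumed rates: about 2% to 14% strictly fewest, and 8% to 21% fewest or tied, for 2 to 10 background events per dose, equal follow-up and two extra serious related events. The second range includes the first; a tie alone accounts for about 6% to 8%. Neither range is the chance that the trial would choose a more harmful dose. That would also require the benchmarks not to identify a superior dose and the AE factor to prevail over the other secondary considerations.

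Equal follow-up is itself an assumption, since the AE counting window is not stated. The plan acknowledges unequal timing for effect sizes ("given the variation in time at post-treatment across MBI doses") but does not mention it for AEs. That is a separate matter, and this point does not rest on it.

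**What to change.** Replace the parenthesis in the harms sentence with an ordered comparison across doses: first serious AEs, with those at least possibly related to the intervention identified; then other AEs at least possibly related to it. Report all AEs by dose alongside, and refer to the AE definitions in the data and safety monitoring plan.

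The cost is about one sentence, plus a seriousness and relatedness classification for each AE. There are two small downsides. Serious related events may be zero in every dose, so the first step may often not discriminate. And relatedness is a judgement made by staff who know the dose, which is why the all-AE table should stay visible beside the ordered comparison.

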Specific Aim 1. Determine the feasibility and acceptability of MBI using videoconferencing for the purpose of improving psychosocial functioning in people with narcolepsy. To carry out Aim 1, we will evaluate the short, standard, and extended doses of MBI on the pre-determined benchmarks below to determine the feasibility and acceptability.

- Benchmark 1 (feasibility of MBI providers): Recruit and train at least 6 qualified providers to deliver the MBI conditions (see section C.4. for details). No specific analyses are planned for this benchmark.
- Benchmark 2 (acceptability of MBI doses): An average attendance ≥ 80% of sessions per MBI condition will be used as a benchmark for determining acceptability of the videoconference delivery of MBI and patient uptake of MBI. This benchmark corresponds to attendance of all sessions (4 out of 4) for the short MBI and 7 out of 8 sessions for the standard MBI. For extended MBI, participants must attend at least 6 out of 8 group sessions plus at least one optional individual session scheduled during provider "office hours" or 7 out of 8 group sessions if no individual sessions are scheduled.
- Benchmark 3 (receipt of MBI targets): The benchmark for receipt of mindfulness and self-compassion will be an increase from baseline to post-treatment in the SCS and FFMQ with an effect size in the moderate range or higher (Cohen's *d* ≥ .5) per MBI dose. This benchmark will be used to evaluate the feasibility that people with narcolepsy are capable of acquiring self-compassion and mindfulness skills from the MBI and also provide estimations of the effect size for each MBI dose (4, 8, 12 weeks). Given that our conceptual model (see Figure 1) posits that self-compassion, mindful awareness, and mindful action are key putative mechanisms by which MBI improves HRQOL, this benchmark will provide an initial test of our conceptual model.
- Benchmark 4 (feasibility of clinical impact): We will use a similar benchmark (*d* ≥ .5) to evaluate the clinical impact from baseline to post-treatment for each MBI dose on the PROMIS global health, depression, anxiety, and psychosocial illness impact measures.

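### Does Benchmark 6 mislead by pooling data completeness over arms that reach post-treatment at 4, 8 and 12 weeks?

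*Combined protocol and SAP*

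**What the plan says.** Under Specific Aim 2, Benchmark 6 asks for "complete data for ≥ 80% of all participants (n=48 out of 60". Each participant is counted up to the post-treatment visit of his or her own arm: "Completion is defined as providing valid data from baseline (A1) through post-treatment for each MBI". On its use, the plan states: "This benchmark will inform the degree of missing data". The same sentence also names the acceptability of the assessment protocol and the choice of instruments, with remote neuropsychological testing and remote actigraphy as examples.

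The Aim 1 benchmarks are set by arm. Benchmark 2 (attendance) is per condition. Benchmark 3 is to "provide estimations of the effect size for each MBI dose (4, 8, 12 weeks", and Benchmark 4 is to "evaluate the clinical impact from baseline to post-treatment for each MBI dose". The secondary considerations of Aim 1 add mixed models to "examine the trend of each MBI dose over time (A1 to A4", and give as the reason that they supplement the effect sizes "given the variation in time at post-treatment across MBI doses". One dose is then selected, and "This MBI program will be used for further testing or optimization".

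**The concern.** Post-treatment comes after 4, 8 or 12 weeks depending on the arm, so the short arm has a third of the extended arm's time in which to lose people. A single count over all three arms describes a mixture that no later trial will run. If the extended dose is selected and its completeness is read off the pooled figure, the next trial could allow too little for missing data.

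The threshold also leaves room for uneven arms. With 20 per arm, 48 is reached by 18 + 16 + 14, which leaves the extended arm at 70%, or by 20 + 16 + 12, which leaves it at 60%.

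A second strand is that Benchmark 6 counts nothing after an arm's own post-treatment visit, although the exploratory models use A1 to A4. If assessments continue after post-treatment, the benchmark could be met while fewer than 80% have the full series.

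**Working it through.** **Plan's own figure.** Five cycles × 12 participants = 60. One group of four per arm per cycle gives 5 × 4 = 20 per arm (equal allocation is implied by Benchmark 5, not stated outright). 0.80 × 60 = 48, which reproduces the stated mark.

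**Size under steady loss.** The documents give no loss rate, so this is an assumed range. Let r = 1 − loss per 4 weeks. Completion to own post-treatment is r, r² and r³ in the short, standard and extended arms, and the pooled value is their mean. At 5%: 0.950, 0.9025 and 0.857, mean 0.903. Enrolment for an illustrative 200 completers is 200/mean or 200/r³, rounded up.

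| Loss per 4 weeks | Pooled | Extended | Gap (points) | Enrolment from pooled | Enrolment from extended |
|---|---|---|---|---|---|
| 3% | 94.1% | 91.3% | 2.8 | 213 | 220 |
| 5% | 90.3% | 85.7% | 4.6 | 222 | 234 |
| 8% | 84.8% | 77.9% | 7.0 | 236 | 257 |
| 10% | 81.3% | 72.9% | 8.4 | 247 | 275 |

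(Gaps are from unrounded values.) The standard arm (94.1%, 90.3%, 84.6%, 81.0%) is close to the pooled figure throughout.

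**Dependence on the shape of loss.** Fix the pooled value at exactly 80% and let part of the loss be unrelated to time.

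| Loss unrelated to time | Extended-arm completion | Extended loss ÷ pooled loss |
|---|---|---|
| 0% | 71.1% | 28.9/20 = 1.45 |
| 5% | 73.1% | 26.9/20 = 1.35 |
| 10% | 75.3% | 24.7/20 = 1.24 |
| 15% | 77.6% | 22.4/20 = 1.12 |

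If all loss is unrelated to time, the ratio is 1. A further possibility is loss that follows group sessions. The standard and extended arms both have eight and the short arm has four, so with 5% loss per four sessions the arms give 0.950, 0.9025 and 0.9025, mean 0.918. The gap for the extended arm is then 0.918 − 0.9025 = 1.6 points, not 4.6.

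**Which figure estimates the extended arm better?** The extended arm's own proportion is unbiased with standard error √[p(1 − p)/20]. The pooled proportion has bias (mean − r³) and variance Σp(1 − p)/(9 × 20). At 5% steady loss:

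- Own arm: √(0.857 × 0.143/20) = 7.8 points.
- Pooled: the variance is (0.0475 + 0.0880 + 0.1223)/180 = 0.00143 and the squared bias is 0.0460² = 0.00211. The root-mean-square error is √0.00354 = 6.0 points.

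| Loss per 4 weeks | RMSE, pooled | RMSE, extended arm alone |
|---|---|---|
| 3% | 4.2 | 6.3 |
| 5% | 6.0 | 7.8 |
| 8% | 8.3 | 9.3 |
| 10% | 9.8 | 9.9 |

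The two are about level at 10%. In interval terms, 16/20 has a 95% Wilson interval of 58% to 92%, and 48/60 has 68% to 88%.

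**Counting through A4.** The weeks of A2 to A4 are not in the supplied text. Suppose they fall at about 4, 8 and 12 weeks in every arm. The chance of reaching 48 as the benchmark is written is P(sum of three Bin(20, pᵢ) ≥ 48). With A1 to A4 required it is P(Bin(60, r³) ≥ 48). At 8% loss these are 89% and 42%; at 10% they are 68% and 14%.

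**A pass mark in each arm.** At a true 80%, P(Bin(60, 0.80) ≥ 48) = 58%, while the chance that all three arms reach 16/20 is 25%.

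**The case for a change.** The strongest case for a change is consistency. The plan sets Benchmarks 2 to 4 by arm and recognises unequal post-treatment timing for effect sizes, but makes no such allowance for completeness. It gives Benchmark 6 a forward-looking purpose and carries one dose forward. A sentence asking for completeness by arm would cost almost nothing. Uneven splits such as 18/16/14 need no assumption about loss to show that 48/60 can hide a weak extended arm.

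Part of this stands. The windows are unequal, the mark is pooled, and under steady loss the pooled figure is optimistic for the extended dose and pessimistic for the short one.

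The rest is weaker. The direction of bias needs loss to grow with calendar time, and the plan's description of the extended arm points partly the other way: it has the same eight group sessions as the standard arm plus optional individual contact, and was designed to improve uptake. Benchmark 6 also covers whether the instruments yield valid data remotely, which need not worsen with course length. The Data Analysis Plan names recruitment pace and effect size as the inputs to future power considerations; it does not say the pooled completeness will size a trial. It also refers to a Statistical Design and Power section that is not in the supplied text, so by-arm reporting cannot be called unplanned.

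On the A1 to A4 strand, mixed models do not need a full series from every participant, and the present definition matches the baseline-to-post-treatment span of Benchmarks 3 and 4.

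**Conclusion.** No change follows. As a feasibility mark for the assessment protocol, 48/60 to each arm's own post-treatment is coherent and reproduces exactly. As a planning figure for the extended dose it could be optimistic by about 3 to 8 points, if loss is steady at 3% to 10% per 4 weeks; by less if some loss does not depend on time; and by nothing systematic if none does.

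Replacing it with the selected arm's own figure trades that bias for the noise of 20 participants, with no gain in root-mean-square error anywhere in that range. Above about 10% loss per 4 weeks the balance would tip the other way. Requiring A1 to A4 would rest on an unseen schedule and, if visits fall at 4, 8 and 12 weeks in all arms, would turn a mark met 89% of the time into one met 42% of the time at 8% loss.

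What remains is a table of completeness by arm with intervals, to be read beside the pooled figure. Analysts can be expected to produce it from data already collected, and it alters neither the Benchmark 6 result nor the choice of dose. All figures assume 20 per arm and an illustrative loss rate, since the documents give none.
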